- A grade 2 or greater immune-mediated adverse event (with the exception of vitiligo) or allergic reactions attributed to talimogene laherparepvec that would require a dose delay of greater than 4 weeks from the date of the planned dose (i.e., approximately 6 weeks from the previous dose). NOTE: immune-mediated glomerulonephritis, vasculitis, and pneumonitis and exacerbation of psoriasis have been observed in subjects receiving talimogene laherparepvec in clinical trials. Most of these subjects had a history of other autoimmune disease and/or prior treatment with agents that offered plausible alternative etiologies, however, immune-mediated adverse events can potentially involve any organ system.
- Any other talimogene laherparepvec-related non-hematologic or hematologic toxicities grade 3 or greater occur that, in the opinion of the investigator, would require a dose

delay of greater than 4 weeks from the date of the planned dose (i.e., approximately 6 weeks from the previous dose).

- The subject develops clinical evidence of any systemic herpes infection (such as encephalitis or disseminated infection).
- A female subject becomes pregnant or fails to use acceptable method(s) of effective contraception (for those subjects who are able to conceive).
- A female subject breast feeds while on study treatment.
- Concurrent medical illness that, in the judgment of the investigator, would make continued treatment with talimogene laherparepvec dangerous for the subject.

For additional information related to special warnings and precautions for the use of talimogene laherparepvec, please refer to the latest version of the Investigator's Brochure.

1.7.6.3. Panitumumab

Toxicities include: Cutaneous reactions (rash, dermatitis acneiform, erythema, dry skin, pruritis, PPE), diarrhea, nausea, electrolyte disturbances (hypomagnesemia, hypocalcemia, hypokalemia), paronychia, ocular disorders, interstitial lung disease, infusion-related reactions, vomiting, constipation, abdominal pain, fatigue, pyrexia, mucositis, and anorexia.

1) Renal impairment

No clinical studies have been conducted in patients with renal impairment.

2) Hepatic impairment

No clinical studies have been conducted in patients with hepatic impairment.

3) Dose Modifications for Dermatologic Toxicity:

Withhold panitumumab for dermatologic toxicities that are grade 3 or higher or are considered intolerable. If toxicity does not improve to \leq grade 2 within 1 month, permanently discontinue panitumumab. If dermatologic toxicity improves to \leq grade 2, and the patient is symptomatically improved after withholding no more than two doses of panitumumab, treatment may be resumed at 50% of the original dose. If toxicities recur, permanently discontinue panitumumab (Table 8). If toxicities do not recur, subsequent doses of panitumumab may be increased by increments of 25% of the original dose until the recommended dose of 6 mg/kg is reached.

Table 8. Panitumumab dose modification for dermatologic toxicity:

Grade	Dose Modification
Grade 1	No dose modification of panitumumab
Grade 2	No dose modification of panitumumab
Grade 3/4	
1st Occurrence: Delay infusion 1 to 2 weeks. If there is improvement, continue panitumumab dose at a 50% of the original dose. If there is no improvement, discontinue panitumumab.
 
2nd Occurrence: Delay infusion 1 to 2 weeks. If there is improvement, continue panitumumab dose at a 40% of the original dose. If there is no improvement, discontinue panitumumab.
 
3rd Occurrence: Delay infusion 1 to 2 weeks. If there is improvement, continue panitumumab dose at a 30% of the original dose. If there is no improvement, discontinue panitumumab.
 
4th Occurrence: Discontinue panitumumab.

In one study [44], dermatologic toxicities occurred in 90% of patients and were severe (grade 3 and higher) in 15% of patients receiving panitumumab. The clinical manifestations included, but were not limited to acneiform dermatitis, pruritus, erythema, rash, skin exfoliation, paronychia, dry skin, and fissures. Monitor patients who develop dermatologic or soft tissue toxicities while receiving panitumumab for the development of inflammatory or infectious sequelae. Withhold or discontinue panitumumab for dermatologic or soft tissue toxicity associated with severe or life-threatening inflammatory or infectious complications. Patients should be advised to avoid sun exposure while receiving panitumumab.

In previous reports, the Common Terminology Criteria for Adverse Events (CTCAE) 4.0 (Table 7) have been used for EGFR-associated rash.

4) Interstitial Lung Disease (ILD)

ILD may be acute in onset and has been observed in 1.3 % of patients, and some cases have been fatal. If patients experience worsening of respiratory symptoms such as dyspnea, cough and fever, panitumumab should be interrupted and the patient should be promptly investigated. If ILD is confirmed, panitumumab should be discontinued and the patient treated appropriately.

5) Electrolyte Abnormalities

Progressively decreasing serum magnesium levels leading to severe (grade 3-4) hypomagnesemia occurred in up to 7% [45] of patients across clinical trials. Monitor patients for hypomagnesemia and hypocalcemia prior to initiating treatment with panitumumab, periodically during treatment, and for up to 8 weeks after the completion of treatment. Other electrolyte disturbances, including hypokalemia, have also been observed. Replete magnesium and other electrolytes as appropriate.

6) Infusion Reactions

In one study [44], 4% of patients receiving panitumumab experienced infusion reactions, and 1% of patients experienced severe infusion reactions (grade 3-4). Infusion reactions, manifesting as fevers, chills, dyspnea, bronchospasm, and hypotension, can occur following panitumumab administration. Table 9 and 10 show the grading criteria for infusion reactions and dose modifications for infusion reactions, respectively. Fatal infusion reactions occurred in post-marketing experience.

Table 9. Grading Infusion Reactions:

	Grade 1	Grade 2	Grade 3	Grade 4
Infusion Reaction	Transient flushing or rash; drug fever <38°C (<100 °F)	Rash; flushing, urticaria; dyspnea; drug fever ≥38 °C (≥100 °F)	Symptomatic bronchospasm with or without urticaria; parenteral medication(s) indicated; allergy related edema/angioedema; hypotension	Anaphylaxis

Table 10. Algorithm for Dose Modifications for Infusion Reactions:

Grade	Dose Modification
Grade 1	Stop the infusion. Consider additional anti-histamines and/or corticosteroid medications. Resume the panitumumab dose at a 50% slower rate. Consider administering prophylactic anti-histamine and corticosteroid medications and/or acetaminophen for subsequent doses.
Grade 2	Stop the infusion. Consider additional anti-histamines and/or corticosteroid medications.

Version Number: v10, March 23, 2023

Protocol Number: #091804

PI Name: [name]

Protocol Title: A Phase I Study of Talimogene

Laherparepvec and Panitumumab in Patients with Locally Advanced Squamous Cell Carcinoma of the Skin (SCCS)

30

RESERVED FOR IRB STAMP
DO NOT MODIFY THIS SPACE

RUTGERS | eIRB
APPROVED

IRB Form Version 12.18.2018

IRB ID: 102018002628

Approval Date: 4/12/2023

Expiration Date: 9/21/2023

	Resume the panitumumab dose at a 50% slower rate. Consider administering prophylactic anti-histamine and corticosteroid medications and/or acetaminophen for subsequent doses.
Grade 3	Stop the infusion. Administer appropriate medical therapy including epinephrine, anti-histamines, corticosteroids, bronchodilators and supplemental oxygen. Observe subject until complete resolution of all signs and symptoms. Permanently discontinue panitumumab.
Grade 4	Stop the infusion. Administer appropriate medical therapy including epinephrine, anti-histamines, corticosteroids, bronchodilators and supplemental oxygen. Observe subject until complete resolution of all signs and symptoms. Permanently discontinue panitumumab. No further study therapy.

All patients will be pre-medicated with diphenhydramine hydrochloride 50 mg (or an equivalent anti-histamine) IV 30-60 minutes prior to the first dose of panitumumab in order to prevent an infusion reaction. At the discretion of the investigator, dexamethasone 20 mg (or an equivalent steroid), and an H2 blocker may also be administered. Approximately 90% of severe infusion reactions occurred with the first infusion despite pre-medication with anti-histamines.

Once the infusion rate has been decreased due to an infusion reaction, it will remain decreased for all subsequent infusions. If the subject has a second infusion reaction at the slower infusion rate, the subject should receive no further panitumumab treatment.

Panitumumab will be immediately and permanently discontinued for serious infusion reactions that are life threatening and/or require hospitalization.

7) Photosensitivity

Exposure to sunlight can exacerbate dermatologic toxicity. Advise patients to wear sunscreen and hats and limit sun exposure while receiving panitumumab.

8) Ocular Toxicities

Keratitis and ulcerative keratitis, both known risk factors for corneal perforation, have been reported with panitumumab. Monitor for evidence of keratitis or ulcerative keratitis. Interrupt or discontinue panitumumab for acute or worsening keratitis.

9) Other Toxicities

Life-threatening and fatal infectious complications including necrotizing fasciitis, abscesses, and sepsis have been observed in patients treated with panitumumab.

Life-threatening and fatal bullous mucocutaneous disease with blisters, erosions, and skin sloughing has also been observed in patients treated with panitumumab.

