Dose modifications will follow the guidelines below. In general, therapy will continue with grade 1 or tolerable grade 2 toxicities. Intolerable grade 2, grade 3, or grade 4 toxicities will result in holding therapy as follows:

1.7.6.1 Dose modification guidelines for talimogene laherparepvec:

Reductions

Dose reductions with regards to changes in the concentrations of talimogene laherparepvec are not permitted. However, patients may require a reduction in the volume injected due to a disease response or due to local toxicity at the injection site. However, if in the course of administration of talimogene laherparepvec the subject cannot tolerate the full dose due to an injection-related adverse event such as pain, the total volume given should be recorded, and the reason for intolerance should be documented as an adverse event.

1.7.6.2. Talimogene Laherparepvec Dosage Adjustments, Delays, Rules for Withholding or Restarting, Permanent Discontinuation:

If talimogene laherparepvec treatment was delayed by > 2 weeks, that dose will be deemed to have been missed and the subject will proceed to the next scheduled treatment visit. Dose reductions of talimogene laherparepvec is not permitted, other than a reduction in the volume injected due to a disease response. CTCAE 4.0 criteria listed in Table 7 are used to determine toxicity grades.

If a subject experience any of the following treatment-related toxicities, talimogene laherparepvec administration should be delayed until the toxicity has resolved to at least CTCAE grade 1 or baseline (Table 7):

- grade 2 or greater immune-mediated adverse events, with the exception of vitiligo.
- grade 2 or greater allergic reactions.
- any other grade 3 or greater hematologic or non-hematologic toxicity.

Table 7. CTCAE 4.0 Criteria:

Symptom	Grade 1	Grade 2	Grade 3	Grade 4
---------	---------	---------	---------	---------

Version Number: v10, March 23, 2023

Protocol Number: #091804

PI Name: [name]

Protocol Title: A Phase I Study of Talimogene
Laherparepvec and Panitumumab in Patients with
Locally Advanced Squamous Cell Carcinoma of the
Skin (SCCS)

26

RESERVED FOR IRB STAMP
DO NOT MODIFY THIS SPACE

RUTGERS | eIRB
APPROVED

IRB Form Version 12.18.2018

IRB ID:

2018002628

Approval Date:

4/12/2023

Expiration Date:

9/21/2023

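### Table 8 tells sites not to modify panitumumab for any grade 2 skin toxicity, while sections 1.7.6 and 1.7.6.3 hold the drug when that toxicity is intolerable

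*Combined protocol and SAP*

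**What the plan says.** Three places in the protocol govern panitumumab dosing when a patient has grade 2 skin toxicity.

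- Section 1.7.6 (Dose Modifications), the lead-in to all the dosing rules, sets the general principle: "In general, therapy will continue with grade 1 or tolerable grade 2 toxicities". It then adds: "Intolerable grade 2, grade 3, or grade 4 toxicities will result in holding therapy as follows".
- Section 1.7.6.3, item 3, gives the panitumumab rule for the skin: "Withhold panitumumab for dermatologic toxicities that are grade 3 or higher or are considered intolerable". Resumption at 50% of the original dose requires grade 2 or lower and that "the patient is symptomatically improved after withholding no more than two doses of panitumumab". Failure to improve to that grade within one month ends panitumumab permanently.
- Table 8, in the same item, has one row per grade. For grade 2 the entry is "No dose modification of panitumumab". For a first grade 3/4 occurrence, in the same column, it is "Delay infusion 1 to 2 weeks. If there is improvement, continue panitumumab dose at a 50% of the original dose".

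On recurrence, the text of item 3 says: "If toxicities recur, permanently discontinue panitumumab". Table 8 allows a second grade 3/4 occurrence to continue at 40% of the original dose and a third at 30%, and discontinues only at the fourth.

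**The concern.** For one clinical situation, intolerable grade 2 skin toxicity, the protocol gives opposite instructions: the text holds the drug and the table gives it unchanged. A dosing table is what site staff are likely to have in hand on the treatment day.

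The situation is foreseeable. Table 7 places acneiform rash with psychosocial impact, or with limits on instrumental daily activities, in grade 2, and a patient could reasonably call such a rash intolerable. Skin reaction is the characteristic toxicity of panitumumab. Section 4.1 B names several recruiting institutions, so the dose given could depend on which part of item 3 a site works from. Safety of the combination is a primary objective, and dosing around this toxicity should be uniform.

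**Working it through.** The plan states no figure on this point and no arithmetic applies. The check takes one case through each rule: dermatologic toxicity of CTCAE grade 2 that is considered intolerable.

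1. **Section 1.7.6.** Intolerable grade 2 is named. Action: hold.
2. **Section 1.7.6.3, text of item 3.** The trigger is grade 3 or higher, or intolerable. Every event of grade 3 or higher is already caught by the first part, so the second part has work to do only below grade 3 and must reach grade 2. Action: withhold.
3. **Table 8, grade 2 row.** Grade is the only key and tolerability does not appear. Action: no modification, so the full 6 mg/kg is given.

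Can step 3 be squared with steps 1 and 2 by saying that a hold is not a dose modification? No. The grade 3/4 entry in the same column begins with an infusion delay, and the withholding rule in the text sits under an item titled as dose modifications. Within this section a delay is a modification, so a row with no modification excludes a hold.

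Does the protocol rank text against table? No statement of precedence was found. The text itself refers the reader to Table 8, and section 1.7.6 says that holding proceeds according to the rules that follow it, which include the table.

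What happens once a grade 2 hold has started? The grade part of the restart condition is met from the outset, so the working conditions are symptomatic improvement and no more than two withheld doses. If both are met, panitumumab may resume at 50%. If not, the text gives no route back to dosing. The text therefore already holds a usable rule for intolerable grade 2, and the table fails to carry it.

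Recurrence, second occurrence at grade 3/4: text, permanent stop; table, delay and, with improvement, 40%. Third occurrence: text, already stopped; table, 30% on the same terms. These entries cannot both be followed.

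**The case against.** The best defence is that tolerability is a second trigger laid over the grade table. Two concordant statements, the section lead-in and the first sentence of item 3, both call for a hold. Table 8 sits directly beneath that sentence, and section 1.3.3 requires the physician to assess toxicity before every cycle. On this reading grade 2 needs no change unless the tolerability override applies, and harm needs a site to use the table while ignoring the paragraph above it.

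Much of this stands. The intended rule is fairly clear, and a careful investigator would hold. But the row as printed gives the wrong action for a case that the text covers expressly, and it carries no cross-reference to the override. Correct dosing should not depend on the reader overruling the table.

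A reader might also infer a second gap: that the one-month limit, "grade 2 within 1 month, permanently discontinue panitumumab", can never trigger for a hold that begins at grade 2, because the threshold is already met, so the patient has no defined stop. The sentence does allow that reading. It also allows the ordinary one, in which a toxicity that has not improved leads to discontinuation. On neither reading is panitumumab given again without symptomatic improvement after at most two withheld doses, and section 6.1.7(d) leaves the investigator a general power to stop. What is missing is at most the label of permanence. That is a minor wording point with no shown dosing consequence.

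**Conclusion.** The contradiction is real and lies in the current text: sections 1.7.6 and 1.7.6.3 agree on a hold, and Table 8's grade 2 row disagrees. It should be corrected because a stated dosing rule gives the wrong action in a foreseeable case.

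At each affected visit the difference is the full 6 mg/kg against no dose. The number of affected visits or patients cannot be derived. Section 1.7.6.3 cites skin toxicity in 90% of patients in one panitumumab study, severe in 15%, and a reader might subtract these to count patients at risk. The difference mixes grades 1 and 2, says nothing about tolerability, and comes from a metastatic colorectal cancer trial, so it does not measure this problem.

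A reader might also infer harm to the dose-limiting toxicity rule, the safety stopping rule or the Simon two-stage decision. The documents give neither a rate of intolerable grade 2 skin toxicity nor a link from these doses to those outcomes, so no such effect is claimed.

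The conclusion rests on two readings: that the tolerability trigger in item 3 reaches grade 2, which section 1.7.6 confirms by naming it, and that a delay counts as a modification, which Table 8 itself shows.

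**What to change.** Split the grade 2 row of Table 8 into two:

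- *Grade 2, tolerable:* no dose modification.
- *Grade 2, intolerable:* withhold; resume at 50% of the original dose only if symptomatically improved after no more than two withheld doses, as in the text; otherwise do not resume.

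This carries the existing restart condition into the table and adds no new threshold.

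In the same amendment, settle recurrence in item 3. Either the text's permanent stop or the table's steps to 40% and 30% can be kept, but text and table must state the same rule. The choice is clinical.

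The cost is one amended table row and one reconciled sentence. Sample size, decision rules and the visit schedule are unaffected.

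### Panitumumab skin-toxicity rules conflict on recurrence: the text of section 1.7.6.3 stops the drug, while Table 8 re-doses at 40% and then 30%

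*Combined protocol and SAP*

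**What the plan says.** Section 1.7.6.3, under dose modifications for dermatologic toxicity, gives a rule in prose. The trigger is: "Withhold panitumumab for dermatologic toxicities that are grade 3 or higher or are considered intolerable". If toxicity has not come down to "grade 2 within 1 month, permanently discontinue panitumumab" applies. Restart at 50% of the original dose is allowed if toxicity is grade 2 or lower and "the patient is symptomatically improved after withholding no more than two doses of panitumumab". On recurrence: "If toxicities recur, permanently discontinue panitumumab (Table 8". Without recurrence, the dose may go back up in steps of 25% of the original dose until 6 mg/kg is reached.

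Table 8 stands directly below. For grade 2 its entry is "No dose modification of panitumumab". For grade 3/4 it sets out a ladder. The first occurrence is a delay of 1 to 2 weeks, then 50% if there is improvement and discontinuation if there is not. The next step is: "2nd Occurrence: Delay infusion 1 to 2 weeks. If there is improvement, continue panitumumab dose at a 40% of the original dose". The third, again after a delay and improvement, is to "continue panitumumab dose at a 30% of the original dose". Only the last is unconditional: "4th Occurrence: Discontinue panitumumab". The table has no re-escalation step.

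Both rules stand in the current version (v10). No statement was found that says which governs.

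**The concern.** A grade 3/4 skin event after restarting at 50% is a recurrence under the text and the second occurrence under Table 8. The text orders a permanent stop. The table orders a delay and, after improvement, another dose. The text names the table as its support, so a reader who follows the reference reaches the opposite instruction.

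This is a safety dosing rule for a toxicity the protocol itself treats as expected with panitumumab. Table 8 covers grade 4 as well as grade 3, and grade 4 acneiform rash in Table 7 extends to extensive superinfection needing intravenous antibiotics or a threat to life. Recruitment runs at several institutions (section 4.1), so two sites, each compliant with the protocol, could treat identical patients in opposite ways.

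**Working it through.** The plan states no figure on this point to reproduce. The check sets the two rules side by side, then works out dose, timing and frequency.

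**1. Comparison**

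| Element | Text, 1.7.6.3 | Table 8 | Can both be followed? |
|---|---|---|---|
| Grade 3/4 recurrence, improved | Permanent stop | 40%, then 30% | No |
| Maximum hold | 1 month, at most two doses withheld | 1 to 2 weeks | Only if 1 to 2 weeks is the usual delay and not a limit |
| Restart criterion | Grade 2 or lower and symptomatic improvement | Improvement, undefined | Yes, if the table abbreviates the text |
| Intolerable grade 2 | Hold (section 1.7.6 agrees) | Grade 2 row makes no change | Yes, if the row is taken as tolerable grade 2 |
| Re-escalation | 25% steps | Not listed | Unclear |

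Only the first row has no reading that reconciles it.

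**2. Dose.** The original dose is 6 mg/kg every 14 days (section 1.7.4.1).
- 50%: 6 × 0.50 = 3.0 mg/kg
- 40%: 6 × 0.40 = 2.4 mg/kg
- 30%: 6 × 0.30 = 1.8 mg/kg

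After an improved second event the next dose is 0 (text) or 2.4 mg/kg (table). After an improved third it is 0 or 1.8 mg/kg. Without improvement both rules give 0.

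**3. Timing.** The first panitumumab dose is on day 22. Suppose the earliest case, with an event after every dose.
- 1-week delays: the 50% dose falls on day 36 + 7 = 43. The next is due on day 43 + 14 = 57, so the 40% dose falls on day 57 + 7 = 64. The 30% dose falls on day 64 + 14 + 7 = 85.
- 2-week delays: day 36 + 14 = 50 for the 50% dose, then day 50 + 14 + 14 = 78 for the 40% dose.

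The 40% dose is thus the third dose by count, but by calendar it comes at about day 64, the planned surgical evaluation, or later. Visit windows of a few days change this little. Section 1.7.11 gives a median of 15 days from first dose to dermatologic or most severe skin/ocular toxicity. That is day 22 + 15 = 37, just after the second planned dose. A first event then moves the sequence on: day 50 + 7 = 57 for the 50% dose and day 57 + 14 + 7 = 78 for the 40% dose. The conflict therefore bears mostly on patients treated around or beyond day 64, in the optional extra cycles (section 1.3) or in continued therapy (section 1.7.3.3).

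**4. Frequency.** The only severe skin rate in the documents is 15% grade 3 or higher, from one cited colorectal study (section 1.7.6.3). The recurrence rate r after re-dosing is not given.
- First events: 30 × 0.15 = 4.5 patients.
- Patients meeting the conflict: 30 × 0.15 × r = 0.45 for r = 10%, 1.125 for r = 25%, 2.25 for r = 50%.
- Chance of at least one such patient, 1 − (1 − 0.15r)^30: about 0.36, 0.68 and 0.90.

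Applying 15% to this population, and every value of r, are assumptions.

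**The case against.** The other side accepts the recurrence conflict and disputes its reach. Much of that stands.

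A reader might infer that the hold time, the restart criterion and intolerable grade 2 are further contradictions of equal weight. The documents do not support that. Table 8 can be read as shorthand for the text's restart criterion. Intolerable grade 2 is held under two explicit statements (sections 1.7.6 and 1.7.6.3), against a table row that does not mention tolerability. The hold times clash only if 1 to 2 weeks is a hard limit. Then a patient not improved at 2 weeks, but at grade 2 or lower and symptomatically improved within a month, would get 3.0 mg/kg under the text and nothing under the table. These are points to align in the same edit.

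Few patients are likely to be affected, and late in treatment. Backstops exist: section 1.7.6.3 separately requires withholding or stopping for severe inflammatory or infectious complications, and section 6.1.7 lets the investigator stop treatment. These lower the expected harm, but they do not tell a site what to do after an uncomplicated second grade 3 event.

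It is also tempting to call the text the safer rule throughout. It is stricter on recurrence, but its hold is longer and it allows re-escalation to the full dose. The amendment log records changes to Table 8, so the table may be the deliberate rule.

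Finally, a reader might see a matching contradiction in the dose-limiting toxicity wording. Section 1.7.9 exempts grade 3 fatigue only if it resolves within 72 hours, while a line in 1.7.9.1 exempts it whatever its duration. That line directly follows the bullet on grade 3 toxicity lasting more than 3 days, in a list specific to talimogene laherparepvec, and reads naturally as a limit on that bullet alone. Grade 3 rash is exempted expressly in 1.7.9. This is a minor clarification, separate from the error here.

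**Conclusion.** The recurrence rule for panitumumab skin toxicity is wrong as written and must be corrected. After an improved second or third grade 3/4 event, the text and the table it cites give incompatible orders: 0 against 2.4 mg/kg, then 0 against 1.8 mg/kg. This follows from the current wording and needs no assumption. The number of patients affected does: about 0.5 to 2.3 of 30, on a borrowed 15% rate and an assumed recurrence of 10% to 50%, mostly around or after day 64. The case for correction rests on a safety instruction that cannot be carried out as written, not on that count.

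A reader might infer that the trial's decision rules are compromised. They are not. The Simon two-stage design does not depend on these rules, and the Table 11 stopping rule counts hospitalizations and delayed or cancelled surgery. The documents give no rate of prolonged grade 3 fatigue, so no effect on the 3+3 assessment can be quantified from them.

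**What to change.** By amendment at all sites:

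1. The sponsor confirms the intended schedule and makes the text of 1.7.6.3 and Table 8 identical on recurrence. The same edit settles the maximum hold (1 month and two doses, or 1 to 2 weeks), the meaning of improvement, the hold for intolerable grade 2, and whether the 25% re-escalation steps remain.
2. Until then, apply the stricter element of each rule. Hold for grade 3/4 or intolerable skin toxicity. Resume at 50% (3.0 mg/kg) only if toxicity is grade 2 or lower and symptomatically improved within the 1 to 2 week delay. Permanently discontinue on a grade 3/4 recurrence. Do not re-escalate.
3. List any patient already re-dosed after a second grade 3/4 skin event.
4. As a minor clarification, state that the fatigue line in 1.7.9.1 limits only the more-than-3-day bullet before it and that the 72-hour rule in 1.7.9 governs. Say in the same place whether the grade 3 rash exemption also applies to that bullet.

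The cost is amendment wording, a notice to sites, and a check of panitumumab dosing records for patients with grade 3/4 skin events. No new procedures or patients are needed.
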